6.1 STUDY POPULATION

The study will consist of up to 1000 patients (up to 800 US, up to 200 Europe) with intermediate-risk and high-risk PE, who meet the eligibility criteria and are appropriate candidates for treatment with the FlowTriever System.

Conservative Therapy Sub-study (US Patients only): In addition to the up to 800 US patients enrolled who will receive treatment with the FlowTriever System, anticoagulation treatment will be evaluated on up to 300 patients diagnosed with intermediate-risk PE, who are not using mechanical thrombectomy as the primary treatment strategy. Approximately 150 of these patients should only be considered intermediate-low risk.

6.2 INFORMED CONSENT

Written, study-specific Informed Consent will be obtained from each patient prior to the patient's de-identified medical record or personal health information (PHI) being shared with any study representative. The Investigator will keep the original Informed Consent Form and a copy will be given to the patient. The patients will be informed that they are free to refuse entry into the study and free to withdraw from the study at any time without prejudice to future treatment.

6.3 POINT OF ENROLLMENT

The FlowTriever System is not being used in an investigational manner and the patient will be treated with the device in the same manner regardless of whether the patient enrolls in the study. Therefore, the patient's consent for treatment is covered under the institution's internal procedures. To participate in the study, the patient must consent to share his/her de-identified personal health information (PHI) with the study sponsor. This allows sites to treat patients prospectively and consent patients after treatment. This can be helpful for sites when the research staff is unavailable to consent the patient prior to the index procedure (i.e., after hours, weekends, holidays). This practice is allowed provided there is no institutional prohibition against post-procedure consent.

Pre-procedure consents are the preferred consenting method and should be obtained within 48 hours of the scheduled index procedure. When the informed consents are obtained retrospectively to the Index procedure, the consent must be obtained after the patient gains full capacity from anesthesia and within 7 days of the index procedure unless approved by a Legal Authorized Representative (LAR).

If utilization of the FlowTriever System is planned, but the FlowTriever device does not enter the patient's vasculature, the patient is not enrolled and as such, his/her data is not entered into the database. The patient is considered enrolled when 1) the patient consents to the study and the device enters the patient or 2) the device enters the patient and the patient consents within 7 days. The timing of the two events, index procedure and consent, are interchangeable.

Conservative Therapy Sub-study (US Patients Only): Point of enrollment will be defined as when 1) the patient is diagnosed with PE and the primary treatment strategy of anticoagulation is administered and 2) the patient consents to the study. The timing of treatment and consent are interchangeable.

6.4 INCLUSION CRITERIA

Patients must meet each of the following criteria to be included in the study:

1. Age \geq 18 years

2. Clinical signs and symptoms consistent with acute PE
3. Echo, CTPA, or pulmonary angiographic evidence of proximal filling defect in at least one main or lobar pulmonary artery
4. Scheduled for PE treatment with the FlowTriever System per the Investigator's discretion*

*US Only Patients enrolled in the Conservative Therapy Sub-study are not required to meet this inclusion criterion but must instead be scheduled for primary anticoagulation therapy as the primary treatment strategy.

6.5 EXCLUSION CRITERIA

Patients will be excluded from the study for any of the following criteria:

1. Unable to anticoagulate with heparin or alternative
2. Diagnosed with a minor PE with less than a 0.9 RV/LV ratio
3. Known sensitivity to radiographic contrast agents that, in the Investigator's opinion, cannot be adequately pre-treated*
4. Imaging evidence or other evidence that suggests, in the opinion of the Investigator, the patient is not appropriate for mechanical thrombectomy intervention (e.g., inability to navigate to target location or predominately chronic clot) *
5. Life expectancy < 30 days, as determined by the Investigator
6. Current participation in another investigational drug or device treatment study that, in the investigator's opinion, would interfere with participation in this study

*US Only Patients enrolled in the Conservative Therapy Sub-study are not required to meet these exclusion criteria.

7 ASSESSMENTS AND FOLLOW-UP SCHEDULE

7.1 SCHEDULE OF ASSESSMENTS

The assessments conducted will be according to normal instructions and care of patients. The Schedule of Assessments comprises recommended and required assessments. Any departures from the follow-up schedule will be documented as a protocol deviation. Required assessments include invasive hemodynamic measurements with HGB during the index procedure*; Echo at baseline, 30 days, and 6 months; dyspnea mMRC score at 48 hours, 30 days, and 6 months; and 6-minute walk test/PEmb QOL at 30 days and 6 months. Missing any of these elements will be documented as a protocol deviation.

**Invasive hemodynamic measurements are not required for patients in the Conservative Therapy Sub-study (US only)*

Wearables Assessment (US Patients Only): In addition to the follow-up schedule, approximately 100 patients receiving treatment with the FlowTriever System and approximately 100 patients receiving anticoagulation treatment will be asked to participate in ongoing data collection utilizing an Apple iWatch. Patients will be provided with a pre-configured Apple iWatch with cellular capabilities at the 48-hour visit. An iPhone is not required to participate. Patients who choose to participate will be expected to wear the Apple iWatch daily, with data collection occurring through their 6-month visit. Data to be collected will include but are not limited to blood oxygen saturation (SpO₂), Heart Rate, and activity. Push notifications via SMS will also require the patient to respond to questions as applicable. Data collected via these means will not be provided to sites, routinely monitored, or used in the clinical decision-making process related to patient health.

Schedule of Assessments

Assessment	Baseline (≤ 48 hrs.)	Procedure* (Day 0)	48 Hours [†] (± 36 hrs.)	30 Days (± 15 days)	6 Months (± 90 days)
Inclusion/exclusion review	X				
Demographics	X				
Medical History and Risk Factors	X				
Clinical Diagnosis (CTEPH, CTED/Post PE Syndrome)	X			X	X
Current PE Condition	X				
Clinical Condition on Arrival to ED/Hospital	X				
Clinical Condition prior to treatment administration	X				
Anticoagulation regimen	X	X	X	X	X
Clinical Labs: HGB, CBC, Troponin, BNP, Lactate, INR, Creatinine, D-Dimer	X	X	X		
Echocardiogram (Required)	X			X	X
CTPA (Requested) [‡]	X				
mMRC Dyspnea Score (Required)	X		X	X	X
Thrombectomy Time		X			
Vitals	X		X	X	X
Invasive hemodynamic measures with HGB, Svo2% (Required)		2X ^Δ			
Pulmonary angiograms		2X			
Bleeding measures		X	X		
FlowTriever Devices used		X			
Access Site information		X			
Procedure Summary (e.g. treatment location, EBL, Fluoro time, clot removal score, HR, pressures)		X			
Adjunctive therapy (thrombolysis and/or additional thrombectomy)	X**	X		X	
6-minute walk test (Required)				X	X
PEmb QOL (Required)				X	X
Adverse event assessment		X	X	X	X
Wearables assessment [§]			X	X	X

* Procedural assessments are not required nor will be captured for patients in the Conservative Therapy Sub-study.

[†] The time to assessment clock starts after TrieverCatheter is removed for the final time.

[‡] CTPA imaging will be performed as per the local standard of care. If a CTPA is ordered, imaging data is requested.

^Δ Invasive hemodynamic measures will include RA, RV, and PA pressures. From the tip of the pulmonary catheter, record the mixed venous PA sat (SvO2), RA pressure, and the PA pressures. Then, flush the catheter and draw the HGB sample from the PA and simultaneously record the heart rate, peripheral artery O2 sat (SaO2), and the oxygen level the patient is receiving. These measurements are obtained pre-FlowTriever insertion and at least 5 minutes after removing the FlowTriever for the final time.

[§] Data collection occurring from the 48-hour visit through the 6-month visit

** (US Patients Only) For Conservative Therapy Sub-study, collect if adjunctive therapy was used at Baseline

NOTE: Consenting can be done 48hr pre-index procedure OR within 7 days post-index procedure. Enrollment occurs when consent is signed AND FlowTriever enters the body. For the Conservative Therapy Sub-study (US Patients Only), consenting can be done 48hr prior to the administration of anticoagulation therapy as the primary treatment strategy OR within 7 days after. Enrollment occurs when consent signed AND the primary treatment strategy to administer anticoagulation has commenced.

NOTE: Please collect COVID status at all visits as applicable on the supplemental EDC form

7.2 BASELINE ASSESSMENTS

An initial evaluation will be used to determine if a patient will be considered for enrollment. Assessments include diagnostic testing that would have been done as part of a patient's routine care. The following must be completed to evaluate for enrollment:

- Review inclusion/exclusion to ensure patient meets criteria
- Review of symptoms
- Confirm PE on echocardiogram or CTPA

If the consented patient meets all eligibility criteria and is scheduled for the thrombectomy procedure as the primary treatment strategy the patient will be enrolled in the study. If the patient consents within 7 days after the thrombectomy procedure and meets all eligibility criteria, the patient will be considered enrolled.

Patients (US Only) being treated with anticoagulation as the primary treatment strategy (instead of FlowTriever) may be invited to participate in the Conservative Therapy sub-study.

The following assessments will be performed at the Baseline Visit within 48 hours of the index procedure. All data must be recorded in the patient's case report forms (CRF):

- Demographic information
- Medical History and risk factors
- Current PE condition
- Clinical condition on arrival to ED/Hospital
- Clinical condition prior to procedure
- Anticoagulation regimen

Clinical laboratory tests are expected to be performed at this visit to establish baseline levels. The panel of tests (including: HGB, CBC, Troponin, BNP, Lactate, INR, Creatinine, D-Dimer) standardly performed at the institution for patients with similar conditions related to PE should be considered.

7.3 INDEX PROCEDURE*

Thrombectomy using the FlowTriever System is considered the index procedure and the treatment phase of the study. The procedure is conducted under fluoroscopic/angiographic guidance. Refer to the Instructions for Use (IFU) for techniques and methods for device deployment. The following data are to be recorded on the patient's Procedure CRF.

- Thrombectomy Time
- Number of FlowTriever devices used, with lot numbers
- Pre- and post-procedure hemodynamics (Invasive hemodynamic measures will include RA, RV, and PA pressures. From the tip of the pulmonary catheter, record the mixed venous PA sat (SvO₂), RA pressure, and the PA pressures. Then, flush the catheter and draw the HGB sample from the PA and simultaneously record the heart rate, peripheral artery O₂ sat (SaO₂) and the oxygen level the patient is receiving. These measurements are obtained pre-FlowTriever insertion and at least 5 minutes after removing the FlowTriever for the final time.)
- Pre- and post-procedure pulmonary angiograms

- Access site information
- Procedure Summary information (e.g. treatment location, EBL, Fluoro time, clot removal score)
- Procedure Bleeding Measures
- Adjunctive therapy (thrombolysis and/or additional thrombectomy)
- Anticoagulation regimen

All procedural angiograms will be uploaded/sent to the sites core laboratory.

7.4 BLEEDING MEASURES

Various bleeding scales have been used to assess hemorrhagic complications after treatment for PE. The current study will capture elements of the commonly-utilized scales.⁶²⁻⁶⁵ This will allow comparisons of the rate of bleeding in the current study to that of other studies that have used a variety of bleeding scales. The elements that are included in several commonly employed bleeding scales are summarized in **Table 1**. Each element of each scale will be collected on the electronic case report forms (eCRFs) so that any of the bleeding scales can be retrospectively tabulated. Bleeding will be measured for 48 hours after conclusion of the index procedure.

Table 1. Elements of Various Bleeding Scales

Elements	Bleeding Scale					
	BARC	PEITHO	VARC	TIMI	GUSTO	ISTH/SSC
Clinically-overt bleeding				X		X
Hemoglobin drop (g/dL) [§]	X		X	X	X	X
Units of transfusion for bleeding [§]	X	X	X		X	X
Hemodynamic compromise		X			X	
Requires surgical intervention	X	X	X			
Life-threatening bleeding [*]	X	X	X			
Fatal bleeding				X		X
Intracranial hemorrhage	X	X	X	X	X	
Intraocular bleed, impairment vision	X					
Chest tube output	X					
Bleeding is actionable [†]	X		X	X		X
Bleeding is in a critical organ			X			X
Compartment syndrome						X

^{*} Includes cardiac tamponade, intracranial bleeding, bleeding requiring intravenous vasoactive agents

[†]Defined by BARC as overt (clinically-evident or observed on imaging) bleeding that leads to discontinuation of a medication (e.g. antiplatelet or anticoagulant), local wound compression or other therapy, leads to hospitalization or prolonging of hospitalization, or to an unscheduled visit to a healthcare professional with laboratory or imaging assessment. Visits not prompting such assessments do not meet the criteria for BARC Type 2 bleeding. Defined by ISTH as hospital admission for bleeding, a physician-guided medical or surgical intervention for bleeding, or a change in antithrombotic therapy.

[§] The numerical hemoglobin drop and/or the number of units transfused will be recorded for all patients. However, neither will be captured as a complication unless they also meet the VARC-2 definition. Both will require a concurrent overt cause of bleeding AND either a ≥ 5 g/dL Hgb drop or ≥ 2 units whole blood/RBC.

7.5 FOLLOW-UP ASSESSMENTS AND WINDOWS

Follow-up evaluation will be scheduled at 48 hours (± 36 hours), 30 days (± 15 days), and 6 months (± 90 days) post-procedure (or post anticoagulation administration for patients enrolled in the Conservative Therapy Sub-study).

The following assessments and procedures will be performed at the 48-hour visit:

- Vitals
- Dyspnea mMRC
- Clinical Labs: HGB, CBC, Troponin, BNP, Lactate, INR, Creatinine, D-Dimer
- Anticoagulation regimen
- Bleeding Measures
- AE observations that occurred since the last visit

The following assessments and procedures will be performed at the 30-day and 6-month visits:

- Vitals
- Clinical Diagnosis (CTEPH, CTED/Post PE Syndrome)
- Echocardiogram
- Dyspnea mMRC
- Anticoagulation regimen
- 6-Minute Walk Test
- PEmb QOL
- AE observations that occurred since the last visit

7.6 UNSCHEDULED FOLLOW-UP VISITS

This Registry study was designed to capture real-world data regarding the clinical use of the FlowTriever System and anticoagulation therapy. Therefore, the study will only record patient visits during the follow-up period that are related to the patient's PE condition and treatment. If a patient returns to the site between scheduled follow-up visits for matters related to the study, the visit will be treated as an unscheduled visit and the assessments completed at this visit will be done at the discretion of the Investigator*. CRF pages are provided for unscheduled visits with appropriate assessments and reason for the visit.

** (US Only Patients) If a patient enrolled in the Conservative Therapy Sub-study requires an unscheduled visit for mechanical thrombectomy utilizing the FlowTriever System, pre-and post-hemodynamic measurements are required to be captured on the Unscheduled Visit CRF.*

7.7 WITHDRAWALS AND LOST TO FOLLOW-UP

Participation is completely voluntary, and each patient is free to withdraw from the study at any time. An investigator also has the right to withdraw the patient from the study in the event of reasons concerning the health or well-being of the patient, or in the case of lack of cooperation. Should a patient decide to withdraw for any reason, or should the investigator decide to withdraw the patient, all efforts will be made to complete and report the observations up to the time of withdrawal as thoroughly as possible. A complete final evaluation at the time of the patient's withdrawal must be made and an explanation given as to why the patient is withdrawing or being withdrawn from the study.

The reason for, and date of, withdrawal must be recorded on the patient's Study Exit CRF. If the reason for the withdrawal is a device-related or procedure-related AE, the event must be reported to the Sponsor and recorded in the CRF.

If the FlowTriever procedure is aborted after entering the vasculature, the patient does not need to complete the follow-up assessments, however, patients who require conversion to open surgery due to incomplete FlowTriever

procedure will be followed for safety through 30 days, or until any treatment-related adverse events resolve, whichever is later. Then the patient will be exited from the study.

All efforts will be made to return patients for all follow-up visits. Due diligence in reaching the patient must be made by two documented telephone contact attempts, emails, or regular postal mail letters. After the above attempts are made, if no response is obtained, the final evaluation of the patient and study exit will be dated on the last visit at which study-related assessments were performed. The Study Exit CRF page will be completed, and communication attempts will be documented.

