5.2.1 Secondary Safety Endpoints

- Individual components of the MAE composite endpoint
- Major access site complications requiring open surgical or endovascular intervention or blood transfusion
- All-cause mortality within 30 days
- Device-related serious adverse events within 30 days

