9.2 REPORTING OF EVENTS

The FLASH Registry study was designed to capture real-world data regarding the clinical use of the FlowTriever System (and anticoagulation treatment in the Conservative Therapy Sub-study) and involves the collection of specific information for research and educational purposes only. It does not specify how the FlowTriever System or anticoagulation will be used to treat PE, and decisions regarding a patient's treatment are not influenced by the study. This is a data collection study only; there is nothing investigational or experimental in the patient's medical treatment.

Therefore, the study will only capture AEs related to the patient's PE condition and its treatment. Reportable AEs include all events considered in the safety analyses (e.g., major bleeding^c), all device- and/or procedure-related AEs, as well as any event resulting in mortality.

The AEs will be captured on the Adverse Event CRF and should include, wherever possible, severity, duration, outcome, the Investigator's description of the event, and his/her medical judgment as to the relationship of the AE (i.e., not related, related, or relationship unknown) to the study device, to the index procedure or any subsequent procedure(s), to a thrombolytic agent or anticoagulant, or underlying disease.

- Non-serious reportable AEs are to be submitted via the electronic data capture system (EDC) in a timely fashion.
- Reportable SAEs must be reported to the Sponsor within 5 business days of the Investigator's knowledge of the event. The event is reported in the EDC.

Appendix 1 includes a list of possible SAEs associated with thrombectomy, including those events considered major device-related events and major morbidity. These events are considered reportable at all time points throughout the study and require submission to the Sponsor and the IRB/EC and regulatory authorities, as required.

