4.0 INCOMPLETE DATE HANDLING AND MISSING DATA

Incomplete dates will follow the following imputation assignment rules:

1. If day is missing but month and year are present, the day will be set to the first date of the month.
2. If both day and month are missing, but year is present, then January 1st will be used as imputed value.
3. If year is missing, then the date is considered missing.

In general, complete case analysis will be used to handle missing values and no other missing data points other than dates will be imputed.

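### Protocol 7.7 lets investigators withdraw patients on health grounds without collecting later vital status or SAEs, which can bias 30-day all-cause mortality downward

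*Protocol*

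**What the plan says.** Protocol 7.7 gives the investigator two grounds for withdrawing a patient: health or well-being, and lack of cooperation. The first is worded as a right to "withdraw the patient from the study in the event of reasons concerning the health or well-being of the patient", and no criteria are attached.

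Once a patient is withdrawn, by either party, the site is to "complete and report the observations up to the time of withdrawal as thoroughly as possible". In addition, "A complete final evaluation at the time of the patient's withdrawal must be made", and the reason and date go on the Study Exit CRF. There is also a reporting duty: "If the reason for the withdrawal is a device-related or procedure-related AE, the event must be reported to the Sponsor". Nothing is required after exit.

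The same section treats one group differently. Patients converted to open surgery after an incomplete FlowTriever "procedure will be followed for safety through 30 days, or until any treatment-related adverse events resolve", whichever is later.

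Three other places bear on this:

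- Protocol 9.2 describes the study this way: "This is a data collection study only; there is nothing investigational or experimental".
- Protocol 5.2.1 and SAP 2.2.1 list all-cause mortality within 30 days and "Device-related serious adverse events within 30 days" as secondary safety endpoints.
- SAP 4.0 says that, in general, "complete case analysis will be used to handle missing values". Only dates are imputed, and no sensitivity analysis for withdrawn patients is planned.

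**The concern.** A health ground for withdrawal is natural where a study imposes a treatment that may have to be stopped. Here there is no study treatment to stop. What ends is the set of study visits and, under the present wording, all data collection, even when the patient has not withdrawn consent.

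A patient withdrawn because of poor health is plausibly at higher risk of dying than one who stays. If such a patient leaves on day 5 and dies on day 15, no provision brings that death into the database. The missingness is then related to the outcome, and complete-case analysis cannot recover a death that was never collected. FLASH has a single FlowTriever arm and descriptive reporting, so the 30-day mortality figure will be read at face value.

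**Working it through.** **Step 1: is there a figure to reproduce?** No. For FLASH the documents give no expected 30-day mortality, withdrawal rate, dropout rate or power calculation. The only usable number is the ceiling of 1000 FlowTriever patients (Protocol 10.1, SAP 5.1). The defect has to be established from the text, and its size can only be illustrated.

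**Step 2: the text side by side.**

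| Patient | Required after leaving or conversion | Source |
|---|---|---|
| Withdrawn by the investigator for health | Data up to withdrawal, final evaluation, reason and date | Protocol 7.7 |
| Withdrawn, with a device- or procedure-related AE as the reason | As above, plus a report of that AE | Protocol 7.7 |
| Converted to open surgery | Safety follow-up to 30 days or AE resolution, whichever is later | Protocol 7.7 |

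Protocol 9.2 makes every death a reportable event and the listed SAEs reportable throughout the study, but it does not extend this past a patient's study exit. The gap at day 30 is therefore real for the first two rows.

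**Step 3: direction and possible size.** Let w be the share withdrawn alive before day 30, m0 the 30-day mortality in retained patients, and mw the mortality by day 30 in withdrawn patients. All three are assumptions.

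- Complete-case rate = m0
- Rate with full vital status = (1 − w) × m0 + w × mw
- Deaths missed = 1000 × w × mw
- Relative understatement = 1 − m0 / rate with full vital status

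Worked example: m0 = 1%, w = 1%, mw = 25% gives 0.99 × 1% + 0.01 × 25% = 1.24%. Deaths missed are 1000 × 0.01 × 0.25 = 2.5, and the understatement is 1 − 1/1.24 = 19%.

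| m0 | w | mw | Complete case | Full status | Deaths missed | Understatement |
|---|---|---|---|---|---|---|
| 1% | 0.5% | 10% | 1.00% | 1.05% | 0.5 | 4% |
| 1% | 1% | 25% | 1.00% | 1.24% | 2.5 | 19% |
| 1% | 3% | 50% | 1.00% | 2.47% | 15 | 60% |
| 4% | 0.5% | 10% | 4.00% | 4.03% | 0.5 | 1% |
| 4% | 1% | 25% | 4.00% | 4.21% | 2.5 | 5% |
| 4% | 3% | 50% | 4.00% | 5.38% | 15 | 26% |

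If mw equals m0, the complete-case rate is unbiased. If withdrawn patients stay in the denominator and are counted as alive, the reported rate is (1 − w) × m0, which is lower still: 0.97% in the third row.

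**Step 4: bounds that need no assumption about mw.** With d recorded deaths and u patients of unknown day-30 status among 1000, mortality lies between d/1000 and (d + u)/1000.

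| d | u = 5 | u = 10 | u = 30 |
|---|---|---|---|
| 10 | 1.00% to 1.50% | 1.00% to 2.00% | 1.00% to 4.00% |
| 40 | 4.00% to 4.50% | 4.00% to 5.00% | 4.00% to 7.00% |

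**The case against.** The strongest reply is that 7.7 grants a permission and nothing shows that it will be used. That stands: the number of such withdrawals is unknown, and at the mild end of the illustration the effect is about 0.05 percentage point or less.

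A health ground also has a legitimate use. Protocol 7.1 requires echocardiography, a 6-minute walk test and a quality-of-life questionnaire at 30 days and 6 months, and a missed one is a protocol deviation. Some patients are also asked to wear a watch daily. Releasing a sick patient from these is reasonable, so the ground should not simply be deleted. It should release the patient from visits without ending data collection.

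A reader might infer more than the documents support:

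- *An AE is a further ground on which the investigator may withdraw a patient.* The AE sentence is a reporting duty. It also covers exits that the patient chooses, and it ensures that the triggering event is captured.
- *Device-related SAEs are undercounted as much as deaths.* A triggering device-related event must be reported, so a patient whose event was already serious counts in a per-patient rate. Only a later first SAE, or later progression to one, is lost. The definition in Protocol 9.1 is also narrow.
- *The primary endpoint is biased.* Its components are intraprocedural or limited to 48 hours, so only a withdrawal inside 48 hours could matter, and only for mortality and bleeding.
- *RV/LV results are distorted by this rule.* Patients too ill to attend lack an echocardiogram whatever 7.7 says, and chart or telephone checks would not supply one.
- *Withdrawn patients leave the mortality denominator.* SAP 3.1 defines the Full Analysis Population as those enrolled, and the complete-case rule is a general one. Neither section says how a withdrawn patient enters the 30-day rate. Leaving them out, or counting them as alive, understates mortality if they die more often than those retained.

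**Conclusion.** The point holds as a gap in follow-up that the protocol permits. As written, 7.7 allows a patient to leave for health reasons and takes no later vital status, while 30-day all-cause mortality is a named endpoint. Any resulting bias is downward, provided withdrawn patients die more often than retained ones.

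Its size cannot be determined from the documents. Under the assumed ranges (w from 0.5% to 3%, mw from 10% to 50%), the relative understatement runs from 4% to 60% when m0 is 1%, and from 1% to 26% when m0 is 4%. The upper ends need many withdrawals with very high mortality, and nothing in the documents supports those values. They should not be read as an expected effect.

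The text does not show that follow-up will in fact end in the patients most likely to die. It shows that the plan does not prevent this. The change is worth making because it is cheap and extends a safeguard that 7.7 already gives one group.

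**What to change.** In Protocol 7.7:

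- Separate stopping study visits and assessments, which may be excused for health reasons, from ending data collection.
- State that health status or an AE does not end data collection.
- Unless the patient withdraws consent, collect vital status and reportable SAEs through day 30, and to 6 months where feasible, by chart or telephone. Protocol 7.8 already accepts some data by telephone.
- First check the consent form. Protocol 13.1 ties consent to the duration of the patient's participation, so its wording must cover collection after visits stop.

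In the SAP:

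- Keep these patients in the denominators for 30-day mortality and device-related SAEs.
- Tabulate withdrawals by reason, which the Study Exit CRF already records.
- Report best-case and worst-case bounds, as in Step 4, for any patient whose day-30 status stays unknown.

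The cost is amended wording and a few extra chart checks or calls. The reported 30-day rates may become slightly less favourable. No treatment changes.
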